Purpose and rationale	To evaluate the efficacy and safety of mavrilimumab versus placebo on top of best standard of care (SoC) in the treatment of COVID-19 pneumonia. As of April 14 2020, COVID-19 has been confirmed in more than 1.8 million people worldwide. Mortality rate has been reported to be approximately 3.7%, which is nearly 4 times higher than that of influenza: there is an urgent need for effective treatment. Accumulating evidence suggests that patients with severe acute COVID-19 pneumonia have a cytokine storm syndrome, or unbalanced hyper-inflammatory response resulting in markedly elevated cytokine and chemokine production. GM-CSF is a cytokine with dual roles as a critical pulmonary hormone and proinflammatory properties that can exaggerate tissue inflammation. GM-CSF-stimulated macrophages produce proinflammatory cytokines, including tumor necrosis factor (TNF), IL-1, IL-6, IL-23, and IL-12. In addition, GM-CSF receptor activation triggers stimulation of multiple downstream signaling pathways; GM-CSF itself can be induced by inflammatory cytokines and in turn augments production of proinflammatory cytokines, thus functioning as a feed-forward inflammatory	

	amplifian Decent analyminamy uncentralled clinical charactions	
	amplifier. Recent preliminary uncontrolled clinical observations	
	on 13 patients in the promoter institution suggest that GMCSF	
	pathway blockade with mavrilimumab is potentially an effective	
	and well-tolerated treatment for COVID-19 pneumonia.	
Primary objective	To evaluate the effect of mavrilimumab versus placebo, added to	
	best SOC, in reducing the dependency on oxygen supplementation	
	in patients with COVID-19 pneumonia and signs of systemic	
	hyperinflammation	
Secondary objectives	• To evaluate clinical outcomes using the 7-point ordinal scale in	
	patients with COVID-19 pneumonia and hyper-inflammation	
	- Time to improvement from the worst clinical status to at	
	least one level of improvement on the 7-point ordinal	
	scale	
	- Duration of hospitalization (days)	
	- Need for admission into intensive care unit (ICU)	
	- Incidence and duration of new mechanical ventilation use	
	during the study	
	• To evaluate the time to resolution of fever if present at baseline	
	 To evaluate the improvement in PaO₂/FiO₂ ratio 	
	• To demonstrate the potential benefit of mavrilimumab in	
	reducing the case fatality rate over 4 weeks among patients	
	with COVID-19 pneumonia and hyperinflammation regardless	
	of other subsequent clinical interventions	
	• To evaluate the in-hospital outcomes in patients with COVID-	
	19 pneumonia and hyperinflammation	
	To evaluate the continuous progression of respiratory failure	
	To evaluate the clinical efficacy of mavrilimumab compared to	
	the placebo by clinical severity stratum (i.e. mild vs moderate	
	subgroup)	
	 To evaluate the proportion of patients requiring rescue 	
	medication during the 28-day period	
	 To evaluate change in laboratory parameters through follow 	
	up	
	 To evaluate changes in clinical serological measurements 	
	related to SARS-CoV-2 infection and to mavrilimumab	
	treatment (i.e.ADA) To evaluate changes in the National Farly Warning Score 2	
	• To evaluate changes in the National Early Warning Score 2	
	(NEWS2):	
	- Change from baseline at day 3, 5, 7, 9, 11, 14, 28;	

Protocol design	 Time to clinical improvement defined as a NEWS2 score of 2 or less maintained for at least 24 hours or discharge, whichever comes first To evaluate the variations in radiological findings in patients that underwent a repeated radiological evaluation, comparing those treated with mavrilimumab to those receiving placebo To evaluate the safety of mavrilimumab in patients with COVID-19 pneumonia: Number of participants with treatment-related side effects, serious adverse events, clinically significant changes in laboratory measures and vital signs This study is a prospective, phase II, multi-center, randomized, double-blind, placebo-controlled trial to evaluate the efficacy and
	safety of mavrilimumab in hospitalized patients with acute respiratory failure requiring oxygen supplementation in COVID-19 pneumonia and a hyper-inflammatory status. The study will enroll patients to mavrilimumab or placebo, in addition to standard of care per local practice, which may include but not limited to anti-viral treatment, hydroxychloroquine, low-dose corticosteroids (≤ 15 mg of prednisone or equivalent) and/or supportive care. The total trial duration will be 12 weeks after initial mavrilimumab or placebo dose. Safety will be closely monitored by a dedicated external data safety monitoring board (DSMB) at regular intervals during the study.
Study population	Approximately 50 patients with diagnosed COVID-19 pneumonia and hyperinflammation will be randomized to mavrilimumab or placebo in a 1:1 ratio
Inclusion criteria	 Adults (≥ 18 years of age) Signed informed consent by any patient capable of giving consent, or, when the patient is not capable of giving consent, by his or her legal/authorized representative or according to local guidelines Patients clinically diagnosed with SARS-CoV-2 virus by PCR or by other approved diagnostic methodology Hospitalized with COVID-19-induced pneumonia evidenced by chest x-ray or CT scan with pulmonary infiltrates Patient requiring oxygen supplementation (i.e. with a SpO2 ≤ 92% while breathing room air) and having a PAO₂/FIO₂ ratio ≤ 300 mmHg

Lactate dehydrogenase (LDH) > normal range and at least one of the following: fever > 38.0 C; increased levels of C-reactive Protein (CRP) $\geq 10x$ ULN mg/L (60 mg/l); or increased levels of ferritin $\geq 2.5x$ ULN (1000 μ g/L) **Exclusion criteria** • Onset of COVID-19 pneumonia symptoms (i.e. dyspnea/respiratory insufficiency) ≥14 days On mechanical ventilation at the time of randomization $A PaO_2/FiO_2 < 100 mmHg$ Uncontrolled systemic infection (other than COVID-19) Hypersensitivity to the active substance or to any of the excipients of the experimental drug Total neutrophil count < 1500/mm³ Severe hepatic cirrhosis History of chronic HBV or HCV infection Known or active tuberculosis (TB) or a history of incompletely treated TB; suspected or known extrapulmonary tuberculosis Moderate/severe heart failure (NYHA Class 3 or 4) Any prior (within the defined periods below) or concurrent use of immunosuppressive therapies including but not limited to the following: Anti-IL-6, anti-IL-6R antagonists or Janus kinase inhibitors (JAKi) in the past 30 days or plans to receive during the study period; Cell-depleting agents (anti CD20) without evidence of recovery of B cells to baseline level; Anakinra within 1 week of baseline; canakinumab within 8 weeks of baseline; abatacept within 8 weeks of baseline. Tumor necrosis factor (TNF) inhibitors within 2-8 weeks (etanercept within 2 weeks, infliximab, certolizumab, golimumab, or adalimumab within 8 weeks), or after at least 5 half-lives have elapsed, whichever is longer; Alkylating agents including cyclophosphamide (CYC) within 6 months of baseline; Cyclosporine (CsA), azathioprine (AZA) or mycophenolate mofetil (MMF) or leflunomide or methotrexate within 4 weeks of baseline. Pregnancy or lactation

	 Any serious medical condition or abnormality of clinical laboratory tests that, in the investigator's judgment, precludes the patient's safe participation in and completion of the study In the opinion of the investigator, progression to death is imminent and highly likely within the next 24 hours, irrespective of the provision of treatments Current participation in any other interventional investigational trials
Study treatment	 Arm 1: Mavrilimumab 6 mg/kg IV infused over approximately 1 hour Arm 2: Matching placebo infused over approximately 1 hour Mavrilimumab or placebo infusions will be prepared and blinded by an unblinded pharmacist or designated staff member. Patients will be randomized according to their age (<50; 50-69; ≥ 70 yo), and their respiratory stratum (PaO₂/FiO₂ 200-300 or 100-199 mmHg) at randomization.
Treatment of interest	Randomized mavrilimumab or placebo as described above. In addition, all patients will receive standard of care per local practice for the treatment of COVID-19-induced pneumonia. The SOC may include but not be limited to anti-viral treatment, low-dose corticosteroids (≤ 15 mg of prednisone or equivalent) and/or hydroxychloroquine or chloroquine and/or supportive care.
Rescue treatment	In worsening patients, treatment with investigational COVID-19 treatments, such as but not limited to antimicrobials, interferon beta, or convalescent serum, is permitted, if approved by the Promoter. Particular attention should be taken when considering rescue treatment with biologic or targeted-synthetic DMARDs/immuno-suppressors due to the risk of potential severe immune-suppression if given in combination with the investigational drug. Systemic corticosteroids (low- or high-dose per medical judgement) could also be used as a rescue medication.
Efficacy assessments	The WHO-adopted 7-point ordinal scale of clinical status will be assessed on a daily basis at baseline and after study treatment during hospitalization as well as at day 7, 14, and 28. NEWS2 score will be assessed on a daily basis at baseline and after study treatment during hospitalization day 7, 14, and 28.

Safety assessments	Adverse event monitoring, physical examinations, and monitoring
	of laboratory safety values.
Other assessments	Standard safety and laboratory assessment (hematology and
	clinical chemistry) will be performed during hospital stay and
	outpatient visits after discharge from hospital (See Schedule of
	Assessments and Procedures Table). In addition, the following
	biomarkers will be determined:
	• hsCRP
	Serum ferritin
	• D-Dimer
	• IL-6 (if available)
Sample Size	Up to approximately 50 subjects will be enrolled. Analysis for
Estimation and	treatment effect will be based on the evaluable population which
Statistical design	includes all subjects who were randomized and received
	mavrilimumab/placebo treatment.
Safety monitoring	To provide safety surveillance of the patients enrolled in the
	study, the external Data Safety Monitoring Board (DSMB) will
	make a blinded monitoring assessment after each increment of
	10 evaluable patients has reached 14 days post-dose.
End of the study and	The follow-up period according to the protocol is 3 months for
timing	each patient enrolled. The end of the study, including statistical
	analysis and drafting of the final report, is expected at 1 month
	from the last follow-up of the last patient enrolled. The study will
	be performed in approximately 3 months, starting from the first
	patient enrolled.
Keywords	COVID-19, acute respiratory failure, mavrilimumab, SARS-CoV-2

2. Background and rationale

2.1. Background

The 2019 novel coronavirus (2019-nCoV; severe acute respiratory syndrome coronavirus 2 (SARS-CoV-2)) has spread rapidly since its recent identification in patients with severe pneumonia in Wuhan, China. As of 14 April 2020, coronavirus disease 2019 (COVID-19) has been confirmed in over 1,800,000 people worldwide, with over 117,000 fatal cases, carrying a mortality rate substantially higher than influenza, which is approximately 1%. There is an urgent need for effective treatment. The clinical spectrum of COVID-19 varies from asymptomatic or pauci-symptomatic forms to clinical conditions characterized by respiratory failure that necessitates mechanical ventilation and support in an intensive care unit (ICU), to multiorgan and systemic manifestations in terms of sepsis, septic shock, and multiple organ dysfunction syndromes (MODS). In one of the first reports on the disease, Huang et al. illustrated that patients (n. 41) suffered from fever, malaise, dry cough, and dyspnea. Chest computerized tomography (CT) scans showed pneumonia with abnormal findings in all cases. About a third of those (13, 32%) required ICU care, and there were 6 (15%) fatal cases. In clinical and epidemiological data from the Chinese Center for Disease Control (CDC) and regarding 72,314 case records (Wu 2020), providing an important illustration of the epidemiologic curve of the Chinese outbreak, the overall case-fatality rate (on confirmed cases) was 2.3%. Of note, the fatal cases were primarily elderly patients, in particular those aged \geq 80 years (about 15%) and 70 to 79 years (8.0%). Approximately half (49.0%) of the critical patients and affected by preexisting comorbidities such as cardiovascular disease, diabetes, chronic respiratory disease, and oncological diseases, died. While 1% of patients were aged 9 years or younger, no fatal cases occurred in this group. 2019-nCoV has affinity for cells in the lower respiratory tract and can replicate there, causing radiological evidence of lower respiratory tract lesions in patients who do not present with clinical pneumonia. There seem to be three major patterns of the clinical course of infection: mild illness with upper respiratory tract presenting symptoms; non-life-threatening pneumonia; and severe pneumonia with acute respiratory distress syndrome (ARDS) that begins with mild symptoms for 7-8 days and then progresses to rapid deterioration and ARDS requiring advanced life support. Mild disease (non-pneumonia and mild pneumonia) occurred in 81% of cases. Severe disease (dyspnea, respiratory rate \geq 30/min, blood oxygen saturation (SpO2) \leq 93%, PaO2/FiO2 ratio [the ratio between the partial pressure of oxygen (partial pressure of oxygen, PaO2) in the blood and the percentage of oxygen supplied (fraction of inspired oxygen, FiO2)] < 300, and/or lung infiltrates > 50% within 24 to 48 hours, occurred in 14% of cases. Critical disease (respiratory failure, septic shock, and/or multiple organ dysfunction [MOD] or failure [MOF]) occurred in 5% of cases.

Among the severe clinical manifestations are severe pneumonia and ARDS. Although the clinical course of the disease seems to predict a favorable trend in the majority of patients, in a percentage of cases still to be defined, after about a week there is a sudden worsening of clinical conditions with rapidly worsening respiratory failure and MOD/MOF. Criteria for definition of specific subpopulations are defined:

- *Severe Pneumonia*. Fever is associated with severe dyspnea, respiratory distress, tachypnea (> 30 breaths/min), and hypoxia (SpO2 < 90% on room air). However, the fever symptom must be interpreted carefully as, even in severe forms of the disease, it can be moderate or even absent.
- Acute Respiratory Distress Syndrome (ARDS). The diagnosis requires clinical and ventilatory criteria. This syndrome is suggestive of a serious new-onset respiratory failure or of worsening of an already identified respiratory picture. Different forms of ARDS are distinguished based on the degree of hypoxia. The reference parameter is the PaO2/FiO2: a ratio SpO2/FiO2 ≤ 315 is suggestive of ARDS.
 - Mild ARDS: 200 mmHg < PaO2/FiO2 ≤ 300 mmHg. In non-ventilated patients or in those managed through non-invasive ventilation (NIV) by using positive end-expiratory pressure (PEEP) or a continuous positive airway pressure (CPAP) ≥ 5 cmH2O
 - *Moderate ARDS*: 100 mmHg < PaO2/FiO2 \le 200 mmHg.
 - Severe ARDS: PaO2/FiO2 ≤ 100 mmHg.

Unfortunately, no drug or vaccine has yet been approved to treat human coronaviruses. Several options can be envisaged to control or prevent emerging infections of 2019-nCoV, including vaccines, monoclonal antibodies, oligonucleotide-based therapies, peptides, interferon, and small-molecule therapies. Although the potential repurposing of existing antiviral agents to treat COVID-19 is already moving into clinical trials, new interventions

based on drugs directly active on the virus itself are likely to require months to years to develop.

Accumulating evidence suggests that a subgroup of patients with severe COVID-19 might have a cytokine storm syndrome, leading to pneumonia, respiratory failure, need for mechanical ventilation, and often death. The identification of hyper-inflammation and treatment using existing therapies that are either in clinical development or approved in other indications with understood safety profiles is a relevant option to address the immediate need to reduce the rising mortality and need for ventilatory support.

In light of pathological findings of pulmonary edema and hyaline membrane formation, timely and appropriate use of drugs aimed at reducing inflammation in a targeted way, together with ventilator support, should be considered for the severe patients to prevent and treat ARDS development.

A cytokine profile resembling secondary haemophagocytic lymphohistiocytosis (sHLH) is associated with COVID-19 disease severity, characterized by increased interleukin (IL)-2, IL-7, granulocyte-colony stimulating factor, interferon- γ inducible protein 10, monocyte chemoattractant protein 1, macrophage inflammatory protein 1- α , and tumour necrosis factor- α . Predictors of fatality from a recent retrospective, multicentre study of 150 confirmed COVID-19 cases in Wuhan, China, included elevated ferritin (mean 1297-6 ng/ml in non-survivors vs 614-0 ng/ml in survivors; p<0.001) and IL-6 (p<0.0001) suggesting that mortality might be due to a dysfunctional hyper-inflammatory response while clearing the virus, i.e. a hyperinflammatory state driven by the host, not the virus (Matthay 2020).

In hyperinflammation syndromes with associated tissue injury, targeted immunomodulation is likely to be beneficial. Re-analysis of data from a Phase 3 randomised controlled trial of IL-1 blockade (anakinra) in sepsis showed significant survival benefit in patients with hyperinflammation, without increased adverse events. Based upon the series of 21 patients treated with tocilizumab reported by Xu, a multicenter, randomized controlled trial of tocilizumab (IL-6 receptor blockade, licensed for cytokine release syndrome), has been authorized in China in patients with COVID-19 pneumonia and elevated IL-6 (ChiCTR2000029765), and tocilizumab has been approved by the SFDA for use in these patients.

In our study, we aim to screen patients with severe COVID-19 pneumonia for hyperinflammation using laboratory trends (e.g., increasing ferritin, or erythrocyte sedimentation rate, C-reactive protein, IL-6 levels) to identify the subgroup of patients for

whomtargeted immunomodulation prevent worsening of pulmonary status, including the need for ventilatory support, with the aim ultimately to improve mortality.

2.2 Rationale for mavrilimumab

GM-CSF strongly activates macrophages and is considered to be a proinflammatory cytokine. GM-CSF production is associated with tissue inflammation. GM-CSF-derived signals are critically involved in the differentiation of macrophages and in the proliferation and activation of other immune cells. GM-CSF-activated macrophages produce proinflammatory cytokines, including tumor necrosis factor (TNF), IL-1 β , IL-6, IL-23 and IL-12. In addition, GM-CSF receptor activation triggers stimulation of multiple downstream signaling pathways, including Janus kinase 2 (JAK2)/signal transducer and activator of transcription 5 (STAT5), the mitogen-activated protein kinase (MAPK) pathway, and the phosphoinositide 3 kinase (PI3K) pathway, all relevant in activation and differentiation of myeloid cells {Hamilton 2002, Shiomi 2015}.

Under physiologic conditions, levels of circulating GM-CSF are low, but levels are elevated in inflammatory conditions. Several cell types can serve as a source of GM-CSF, including fibroblasts, endothelial cells, macrophages, dendritic cells, T cells, neutrophils, eosinophils, and cancer cells, with most production occurring locally at the site of inflammation {Shiomi 2015}. This in turn exacerbates the inflammatory reaction via cytokine pathways that have been termed the colony stimulating factor network. GM-CSF can be induced by inflammatory cytokines and in turn augments production of proinflammatory cytokines, thus functioning as a feed-forward inflammatory amplifier {Hamilton 2002}.

Zhou et al (2020) recently reported elevated levels of GM-CSF in the lungs of patients with COVID-19, specifically showing that after the 2019-nCoV infection, CD4+T lymphocytes are rapidly activated to become pathogenic T helper (Th) 1 cells and generate GM-CSF, etc. The cytokine environment induces inflammatory CD14+CD16+ monocytes with high expression of IL-6 and accelerates the inflammation. The authors further contend that these aberrant and excessive immune cells may enter the pulmonary circulation in huge numbers and play an immune-mediated damaging role, causing lung dysfunction and quick mortality.

GM-CSF signals through GM-CSF-R, which consists of a specific ligand-binding α -chain (GM-CSF-R α) and a signal-transducing β -chain (GM-CSF-R β) that is common to IL-3 and IL-5 receptors. Hence, GMCSF-R signaling can be specifically targeted with antibodies directed at GM-CSF-R α (Crotti 2017). Mavrilimumab is an anti-GM-CSF-R α monoclonal antibody (human isoform IgG4) previously developed by MedImmune and now in development by Kiniksa that has been shown to inhibit the GM-CSF signaling axis in humans and improve clinical outcomes measures in a Phase 2 program in Rheumatoid Arthritis {Burmester 2011}.

2.4 Purpose of the study

The purpose of this study is to evaluate the efficacy and safety of mavrilimumab in the treatment of hospitalized patients with COVID-19-induced pneumonia and systemic hyperinflammation. The study will also evaluate the morbidity and mortality rate in patients with COVID-19 due to the inflammatory response to SARS-CoV-2 treated with SOC in the control arm.

3. Study objectives and endpoints

3.1 Primary objective and primary endpoint

Primary objective	Primary endpoint
To demonstrate the benefit of mavrilimumab vs placebo added to best SOC in reducing the dependency on oxygen supplementation in patients with COVID-19 pneumonia and signs of systemic hyperinflammation	Time to the absence of need for oxygen supplementation (time to first period of 24 hrs with a SpO ₂ of 94%) within day 14 of treatment, stated as Kaplan-Mayer estimates of the proportion of patients on room air at day 14 and median time to room air attainment in each arm.

3.2 Secondary objectives and secondary endpoints

Secondary objective	Secondary endpoints
To evaluate clinical outcomes using the 7-point ordinal scale (APPENDIX 1) in patients with COVID-19	- Proportion of responders at day 7, 14, and 28 based on the 7-point ordinal scale. Response is defined as a 7-point ordinal scale of 3 or less, i.e. no supplemental oxygen
	 Time to response, defined as time from date of randomization to the date with a 7-point ordinal scale of 3 or less, i.e. no supplemental oxygen
	- Proportion of patients with at least two-level improvement in clinical status at day 7, 14, and 28
	- Baseline change of clinical status to day 7, 14, and 28
To evaluate the time to disappearance of fever if present at baseline	Time to resolution of fever (for at least 48 hours) in absence of antipyretics, or discharge, whichever is sooner in the 4-week period after

IRCCS San Raffaele Scientific Institute Protocol (v 3.1 – 01 mag 2020)

	study treatment. Resolution of fever is defined as body temperature:
	- ≤36.6°C (axilla) or
	- ≤37.2 °C (oral), or
	- ≤37.8 °C (rectal or tympanic)
	Note: Fever is defined as defined as body temperature > 37.4°C [axilla], or > 38.0 °C [oral], or >38.4°C [rectal or tympanic].
To demonstrate the potential benefit of mavrilimumab in reducing the case fatality rate over 4 weeks among patients with COVID-19 pneumonia and hyperinflammation regardless of other subsequent clinical interventions	COVID-19-related death during the 4-week period after study treatment (in hospital and overall)
To evaluate the in-hospital outcomes in patients with COVID-19 pneumonia and hyperinflammation	Proportion of hospitalized patients who died or required mechanical ventilations (WHO Categories 6 or 7) by day 14
To evaluate change in laboratory parameters through follow up	Variations of the following serological markers over follow-up:
	- C-reactive protein
	- Ferritin
	- D-Dimer
To evaluate changes in the National Early Warning Score 2 (NEWS2, Appendix 2)	- Median changes of NEWS2 score from baseline at day 7, 14, 28 (or discharge, whichever comes first)
	- Time to clinical improvement (as defined as a NEWS2 score of 2 or less maintained for at least 24 hours or discharge, whichever comes first)
To evaluate the variations in radiological findings in patients that underwent a repeated radiological evaluation, comparing those treated	Variations from baseline to subsequent timepoints (when available) in terms of percentage of lung involvement, modifications in

with mavrilimumab to those receiving placebo

the normal parenchyma, ground glass opacities (GGO), crazy paving pattern, parenchymal consolidations, and evolution towards fibrosis.

Analysis will be centralized and performed by at least two independent radiologists, also by means of the IntelliSpace Portal, version 7 (Philips Medical Systems).

To evaluate safety of mavrilimumab in patients with COVID-19-induced pneumonia and systemic hyperinflammation

Number of patients with treatment-related side effects (as assessed by Common Terminology Criteria for Adverse Event (CTCAE) v.5.0), serious adverse events, adverse events of special interest, clinically significant changes in laboratory measurements and vital signs

To evaluate additional outcomes in patients with COVID-19 pneumonia associated with systemic hyperinflammation

To evaluate additional outcomes in patients with COVID-19 pneumonia associated with systemic hyperinflammation such as:

- the duration of hospitalization (days);
- the need for admission into intensive care unit (ICU) and it median duration, if applicable;
- the incidence and median duration of new mechanical ventilation use during the study, if applicable;
- the continuous progression of respiratory failure as evaluated by the PaO_2/FiO_2 ratio in the 28-day period or until discharge, whichever comes first;
- the proportion of patients requiring rescue medication during the 28-day period, if applicable.

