8.1 Schedule of Assessment and Procedures (table 1)

	(0-24 hrs prior to dose)	(investigational drug dosing)	п	hospitalization until day 28 or discharge (whicever is earlier)	7*	14*	28 (or at discharge)*	*34 -/+	(+- 7 days) End of study*
		S	T U D	YPEF	R I O	D		FOLLOW	U P
informed consent	×								
Inclusion/exclusion criteria	×	x(2)							
Demographics / medical history /relevant comorbidities	×								
SarsCoV-2	x(1)	REC	CORD ALL SA	RECORD ALL SARS-COV-2 DETERMINATIONS AS OBTAINED	S AS OBTAIN	ED	×	x (if available)	x (if available)
Vital signs (HR, RR, SpO2 and/or PaO2, BP, body temp)	×	x(2)	×	×	×	х	×		
Oxygen delivery (flow + FiO2)	×	x(2)	×	×	×	×	×	×	×
NIV use (hours/day)	×	x(2)	×	×	×	×	×		
Height, weight	×								
Physical		5(2)	S						
Clinical status with the 7-point ordinal scale		x(2)	×	×	×	×	×	×	×
Vital status (and if applicable, cause of death)			×	×	×	×	×	×	×
Blood cultures (Aer/Anaer)		x(3)							
Hematology (Hb, MCV, WBC, Plt, absolute count of N,L,M,E,B)	×		×	x every other day until discharge	×	×	×	x (if available)	x (if available)
Clinical chemistry (AST, ALT, ALP,									
LDH, creatine kinase, troponin,	>		>	x every other day until	,	>	,	v (if everience)	(aldelieve fi) v
chicoco total protoin CBD forritin	<		<	discharge	<	<	<	v (II available)	A (II available)
glucose, total protein, chr., refritiil, D-dimer; IL-6 [if available])									
Pregnancy test (if applicable)	S								
CT scan / chest X-ray	x(1)		RECORD ALL	RECORD ALL PULMONARY IMAGING AS OBTAINED	OBTAINED		x (if available)		
Electrocardiogram	S(1)								
Adverse events	×	x(2)	×	×	×	×	×	×	×
Prior / concomitant medications	×	x(2)	×	×	×	X	×	×	×
Randomization		x(2)							
Study drug administration		x(2)							
In-hospital outcomes:									
Days on non-invasive ventilation		x(2)	×	 	 	 	×		
Days on mechanical ventilation		x(2)	 	 		 	×		
Days in hospital		x(2)	×	×		×	×		
Days in ICU		x(2)	×	×		×	×		
Days with use of supplemental O2		x(2)	×	×		×	×		
Days on ECMO		x(2)	×	×		×	×		
Blood collection for experimental		x(2)		x (day 5)	x (if	x (if	x (if possible)	x (if possible)	x (if possible)

x to be recorded into the eCRF

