Adverse events of neutropenia of special interest are defined as an ANC < 1.0×109 cells/L. Investigational product will not be administered to any subject who has an ANC < 1.0×109 cells/L. Administration of investigational product may continue in the event that the ANC > 1.5×109 cells/L and following agreement with the medical monitor.

Serious Infection

Grade 3 severity infections that require treatment with IV therapy (antibiotics, antiviral, or antifungal) and opportunistic infections will be considered serious even if they do not require in-patient hospitalization. Every effort should be made to identify the causative pathogen through prompt and appropriate investigation by the investigator or reporting physician.

Pregnancy reporting

Women should use effective contraceptives during treatment with mavrilimumab and for up to 3 months after dosing.

If a female trial participant becomes pregnant, the study should be stopped, and the trial participant must be asked to read and sign pregnancy consent form to allow the Study Doctor ask about her pregnancy. To ensure participant safety, each pregnancy occurring after signing the informed consent must be reported to the Promoter within 24 hours of learning of its occurrence. The pregnancy should be followed up to determine outcome, including spontaneous or voluntary termination, details of the birth, and the presence or absence of any birth defects, congenital abnormalities, or maternal and/or newborn complications.

Pregnancy should be recorded and reported by the investigator to CMO & PS. Pregnancy follow-up should be recorded on the same form and should include an assessment of the possible relationship to the study treatment any pregnancy outcome. Any SAE experienced during pregnancy must be reported.

Reporting of study treatment errors including misuse/abuse

Medication errors are unintentional errors in the prescribing, dispensing, administration or monitoring of a medicine while under the control of a healthcare professional, participant or consumer (EMA definition).

Misuse refers to situations where the medicinal product is intentionally and inappropriately used not in accordance with the protocol.

Abuse corresponds to the persistent or sporadic, intentional excessive use of a medicinal product, which is accompanied by harmful physical or psychological effects.

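### The only secondary endpoint that isolates mortality counts COVID-19-related deaths, although its objective is the 4-week case fatality rate with no stated limit on cause

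*Protocol*

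**What the plan says.** The mortality objective in section 3.2 begins "To demonstrate the potential benefit of mavrilimumab in reducing the case fatality rate over 4 weeks among patients" and ends with the qualifier "regardless of other subsequent clinical interventions". The synopsis states the same objective. Neither place limits the cause of death.

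The endpoint paired with it is "COVID-19-related death during the 4-week period after study treatment (in hospital and overall". The words in brackets describe where the death occurred; they do not widen the cause. The protocol does not say how a death is judged to be related to COVID-19.

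Death of any cause enters other parts of the plan:

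- Category 7 of the ordinal scale (section 8.4 and Appendix 1) is death without qualification. It feeds the responder, two-level improvement and change endpoints up to day 28.
- A separate secondary endpoint is "Proportion of hospitalized patients who died or required mechanical ventilations (WHO Categories 6 or 7) by day 14".
- Fatal events are serious adverse events, reported regardless of causality (section 10.1), and serious adverse events are part of the secondary safety endpoint.
- Table 1 (section 8.1) has a row "Vital status (and if applicable, cause of death", marked from after dosing to the end-of-study visit.

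On foreseeable harms, the adverse events of special interest in section 10.1 include hypersensitivity, pulmonary abnormality, neutropenia and serious infection. For the last of these, "Grade 3 severity infections that require treatment with IV therapy (antibiotics, antiviral, or antifungal) and opportunistic infections will be considered serious".

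**The concern.** The objective asks how many patients die within 4 weeks. The endpoint asks how many die of the disease. The two differ by the deaths that are put down to something else, and for an immunomodulator some of those deaths may be caused by the treatment. A cause-specific count scores such a patient in the same way as a survivor.

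The attribution is also difficult in this population. Section 2.1 lists sepsis, septic shock and multiple organ dysfunction among the manifestations of COVID-19 itself, so separating a fatal course of the disease from a fatal superinfection is a matter of judgement. Section 6.3 adds that combining the study drug with certain rescue agents carries a risk of severe immunosuppression.

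At stake is the one endpoint that readers would take as the trial's mortality result. It could show fewer deaths on mavrilimumab when survival is equal, or hide an excess.

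**Working it through.** **1. The plan's own figure.** The mortality endpoint has no planned event rate, power or sample size. The only sizing figure (section 11.1) is for oxygen independence: 83% against 40% by day 14, two-sided alpha 0.05, 90% power, 28 events. It reproduces:

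- Hazard ratio under exponential times: ln(1 − 0.83) / ln(1 − 0.40) = 3.469.
- Schoenfeld events: 4 × (1.960 + 1.282)² / (ln 3.469)² = 27.2, rounded up to 28.

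This check supplies nothing on mortality. What carries over is the size: about 50 patients at 1:1, so about 25 per arm.

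**2. Does another endpoint fill the gap?**

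| Endpoint or data | Any-cause death counted? | Isolates death? | Reaches day 28? |
|---|---|---|---|
| Mortality endpoint (3.2) | No, COVID-19-related only | Yes | Yes |
| Ordinal-scale responder (3.2) | Yes, as non-response | No, merged with still needing oxygen | Yes |
| Change in ordinal status (3.2) | Yes, as category 7 | No | Yes |
| Death or ventilation composite (3.2) | Yes | No, merged with ventilation | No, day 14 |
| Primary endpoint (11.2) | Death censored at day 14 | No | No |
| Serious adverse events (3.2, 10.1) | Yes | Not an all-cause mortality comparison | Yes |

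No row answers yes in all three columns.

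**3. Size of the distortion.** Let D be all-cause deaths and r the deaths judged not related to COVID-19, with subscripts m for mavrilimumab and p for placebo, and 25 patients per arm.

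- True difference (placebo minus mavrilimumab) = (D_p − D_m) / 25.
- Difference in the endpoint = [(D_p − r_p) − (D_m − r_m)] / 25 = true difference + (r_m − r_p) / 25.

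The distortion is therefore 4 percentage points × (r_m − r_p), since 1/25 = 4%. It is zero when the same number is excluded in each arm.

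**4. Illustration.** The death counts are assumed. Take 4 all-cause deaths in each arm (16% against 16%) and r_p = 0:

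| Mavrilimumab deaths judged not related | Endpoint, mavrilimumab vs placebo | Apparent benefit | Fisher p |
|---|---|---|---|
| 1 | 12% vs 16% | 4 points | 1.00 |
| 2 | 8% vs 16% | 8 points | 0.67 |
| 4 | 0% vs 16% | 16 points | 0.11 |

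In the other direction, an all-cause excess of 6 against 4 deaths (24% against 16%) becomes 4 against 4, no difference, if two of the mavrilimumab deaths are judged not related.

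**5. Does blinding remove this?** Blinding (section 6.7) keeps assessors from labelling deaths differently because they know the arm. It makes r_m and r_p equal in expectation only if deaths of the kind judged not related are equally frequent in both arms. If the drug causes some of them, r_m exceeds r_p even with perfect blinded attribution.

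**The case against.** Five points can be made for the plan.

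- **Case fatality may mean death from the disease.** Section 2.4 shows an interest in mortality driven by the inflammatory response. Section 2.1, however, uses case fatality over confirmed cases with no cause limit, and the objective states none. It stands that this is a mismatch and a poor choice of endpoint rather than a flat contradiction.
- **The qualifier in the objective does not concern cause of death.** A reader might infer that "regardless of other subsequent clinical interventions" rules out a cause-specific endpoint. It does not: the phrase refers to later treatment, such as rescue, and COVID-19-related death can be counted whatever rescue was given.
- **The deaths are not lost to the trial.** A reader might infer that infection deaths disappear from the comparison of arms. They do not: they count in the ordinal scale, the day-14 composite and the safety endpoint, and the external safety board reviews safety. This stands in full, and the point is limited to the one endpoint.
- **Related is a wide word and assessors are blinded.** Many superinfection deaths within 4 weeks might be judged related, and attribution rules may sit in an analysis plan that is not shown, so their absence is no finding. This makes the distortion less likely but does not exclude it.
- **Mortality is only descriptive here.** With about 25 per arm, none of the differences in the first illustration would be significant. True, but a small phase II trial is read largely on its point estimates.

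**Conclusion.** The point holds for one secondary endpoint. The only endpoint that isolates mortality leaves out deaths judged unrelated to COVID-19, its objective gives no reason to do so, and no other listed endpoint gives a 28-day all-cause comparison. The plan itself names the kinds of harm that could produce such deaths on the active arm.

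The distortion is 4 percentage points for each death excluded from one arm beyond the other. This assumes 25 evaluable patients per arm. Whether any such death will occur, and in which arm, cannot be taken from the protocol, which states no mortality rate. The illustrations show what the definition permits and do not predict a result; reading an expected halving of mortality into them would go too far. The primary endpoint and the sample size are not affected.

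**What to change.** In section 3.2, define the mortality endpoint as death from any cause within 4 weeks of study treatment, in hospital and overall. Keep the existing time origin; nothing here calls for moving it. Report COVID-19-related death beside it as a supportive result.

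The cost is one line of text. Table 1 already records vital status and cause of death, and the ordinal scale collected by phone after discharge has death as a category, so no new data are needed. The method for binary endpoints in section 11.2 applies unchanged. All-cause death also removes the need for a judgement on cause in the main mortality result.
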